Recruitment Our previous BPA consumption, and other feeding and exercise trials showed that recruitment of normal-weight, sedentary participants are extremely feasible with limited participants lost to follow-up (>98% retention).²⁹⁻³³ In the current study, we anticipate similarly high retention. We will employ comparable retention procedures, including financial incentives (\$500 total) for completing all visits. The breakdown of participant payment is: Baseline testing = \$100, Treatment days = \$400. During the treatment phase for 4 days participants will have a safety blood draw (see below for more detail) to assess liver, kidney and immune function at the Cal Poly Health Center. Cal Poly students will be charged \$7.50 per draw (total \$30). However, treatment days compensation will be increased to \$430 to cover these costs if the participant is a Cal Poly student.

BPA Dose and Duration The dose of BPA selected in the proposed study is consistent with the US EPA reference dose of 50 µg/kg body weight. The National Toxicology Program reported that that typical BPA exposures range from 0.43 to 1.5 µg/kg body weight.³⁴ Based on occupation work, BPA exposure can be as high as 100 µg/kg body weight however.³⁴ The BPA dose selected is well below the FDA **no-observed-adverse-effect level** of 5 mg/kg BW per day.³⁵ The pharmacokinetics of 50-100 µg/kg BW of BPA has a blood concentration max occurring at ~1 hour after consumption, 92% of BPA is present in urine at 24 hours, and urinary half-life of 4-5.5 hours, with no reported side effects.³⁶⁻³⁸ Our preliminary oral BPA consumption protocol at 4 µg/kg BW and 50 µg/kg BW had no gastrointestinal distress or subjective appetite changes. Thus, we anticipate no long-term negative effects of BPA consumption at 50 µg/kg BW as this is the reference dose in humans per the US EPA. Nevertheless, we will have medical supervision by [name] (Board certified internist at the Cal Poly Health Center), throughout the entire study and will assess four hepatic function tests, one at baseline and three during treatment on days 4-6. Also, after completion of the study, all subjects will be offered a 2-day “fresh food” diet that has been shown to reduce BPA exposure by 66%,²⁸ or will be provided with a \$50 gift card to a natural food market (participant will choose). In our previous BPA consumption study, we successfully used a similar protocol to limit BPA exposure after completion of the study.

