participant to lay flat on their back without moving for approximately 10 minutes. Cell mutation can occur with excessive exposure to radiation, however the Lunar iDXA has technology that enables extremely precise and safe measurements. It uses a unique “K-edge filter” that absorbs X-rays to protect the patient against unnecessary exposure, resulting in a low radiation exposure of approximately 0.0003 mSv per scan. The exposure from one scan is equivalent to 17.6% of the average person’s daily exposure to radiation. For comparison, a normal chest X-Ray causes .010 mSv of radiation exposure per scan which is 588% of an individuals average daily exposure. There are no complications expected with the DXA procedure.

After preliminary tests, a 2-day run-in baseline energy balance diet low in BPA will occur (see Figure 2 above) in which 24-hour urine, fasting blood, muscle insulin sensitivity, hepatic glucose suppression and fecal microbiome will be assessed. Participants will then be randomized (blocked by sex and ethnicity) to either Diet+BPA or Diet+No BPA, in a double-blinded fashion. Similar to our previous intervention studies, the study statistician ([name]) will computer generate the randomization scheme but will not have contact with any participant. Repeated assessment of 24-hour urine collection of BPA for 3 consecutive days, and fasting blood, muscle insulin sensitivity, hepatic glucose suppression, and gut microbiome will occur at the end of the treatment period. Consumption of the final BPA or placebo will occur 1 hour prior to the muscle insulin sensitivity measurement and glucose stable isotope infusion.

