Adequacy of Protection Against Risks. Risks will be minimized by continuous safety monitoring, highly qualified staff, careful screening prior to enrollment, and by our medical board-certified internist consultant ([name]). [name] will be on call during the study. We are using standard laboratory techniques that we have used extensively in our prior studies; laboratory staff is experienced in all these testing procedures using the CDCs universal precautions standards. All laboratory staff is trained in CPR.

Blood draws and hyperinsulinemic euglycemic clamp technique. The PI has studied diabetes and appetite regulation for over 18 years and has extensive experience with blood draws and assessment of insulin action. The total amount of blood taken for the entire study is relatively small, only about 70 ml. There are some minor risks involved with catheters and blood draws. To minimize these risks, we will follow the CDC universal precautions in preventing transmission of agents in health care settings. Catheters will only be inserted by trained individuals (e.g. phlebotomist), using sterile technique at all times. There may be some pain associated with the needle stick at the moment of insertion, followed by minor discomfort of having the needle withdrawn and the catheter advanced slightly into the vein. There may potentially be a local infection, slight bleeding, or bruising, and fainting in some participants. To minimize this, subjects will be sitting for all blood draws and during the clamp. Moreover, [name] (medical consultant) will be “on call” during all clamps. The study staff and [name] will be available for emergencies and will refer and help participants obtain appropriate medical care, if needed.

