Bisphenol A Consumption. As mentioned above, the BPA dose selected is well below the **no-observed-adverse-effect level** of BPA of 5 mg/kg body weight per day, according to the U.S. FDA³⁵ and is reference dose as reported by the US EPA.¹⁹ Our preliminary study examined the effects of varying doses of BPA consumption, including 50 $\mu\text{g}/\text{kg}$ body weight, on markers of type 2 diabetes. We observed no gastrointestinal distress side effects, or changes in subjective appetite ratings with this or a smaller dose. Pharmacokinetics studies of similar dosages (50-100 $\mu\text{g}/\text{kg}$ body weight) of BPA have also reported no side effects, no adverse effects, or no unintended participant harms.³⁶⁻³⁸ Because this proposed study is relatively short (4 treatment days), we anticipate no long-term negative effects of BPA given that the dose is within a typical exposure range seen in US adults. We will provide all participants with a 2-day “fresh food” diet after they have completed the study (or drop out during the study). A similar “fresh food” diet has been shown to reduce urinary BPA concentrations by 66%.²⁸ To minimize risks, medical supervision will occur throughout the study and we will now expand daily blood tests to include both liver, kidney, and immune functioning. In the morning during all treatment days a Comprehensive Chemistry Panel (liver and kidney functioning) and Complete Blood Count test will be completed and evaluated by [name]. The Comprehensive Chemistry

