Data Safety Monitoring Plan. The data safety-monitoring plan for this trial focuses on close monitoring by the PI/Co-Is, IRB, and consultants. The Safety Officer Report template will be finalized with input from the entire investigative team at the time of award. The investigative team will review quarterly recruitment, retention, and safety information on all participants, including any adverse events and unintended harms. Daily/weekly internal investigator meetings will also occur to review recruitment, attendance, retention, and safety data on an ongoing basis. Annual DSMB meetings, via conference call, will occur with the entire research team. **Adverse Events/ Reporting of Events:** The investigators are responsible for reporting all adverse events, serious adverse events, and unintended harms within pre-specified times to the DSMP and IRB. Adverse events will include any event that causes or increases risk of harm to the subject or others. Serious adverse event will include any event that results in death, inpatient hospitalization or prolongation of existing hospitalization, a persistent or significant disability or incapacity, or a congenital anomaly. A fatality will be reported immediately. Adverse events reported at an assessment visit or informally at any time will be evaluated by the investigators to determine if they are unanticipated problems involving risk to subjects and others or not. The subject's situation will also be assessed with regard to study and/or intervention continuation. The Postdoctoral Research Fellow, reported to the PI and investigative team, the DSMP, and the IRB, will record any serious adverse event. American Diabetes Association and/or National Institutes of Health will be informed of serious adverse events and actions taken.

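### No dated adverse-event question follows the final dose and clamp, so events arising after the participant leaves are recorded only if volunteered

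*Combined protocol and SAP*

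**What the plan says.** The stay is six days: two of run-in and four of treatment (Overview). On the final dose, Sequence of Events says: "Consumption of the final BPA or placebo will occur 1 hour prior to the muscle insulin sensitivity measurement and glucose stable isotope infusion". The same section puts the repeat urine, fasting blood, clamp and microbiome assessments at the end of treatment.

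Safety bloods are described twice. Under BPA Dose and Duration the team "will assess four hepatic function tests, one at baseline and three during treatment on days 4-6". Under Bisphenol A Consumption the schedule is "In the morning during all treatment days a Comprehensive Chemistry Panel", together with a blood count. Neither names a test after the treatment days.

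The Data Safety Monitoring Plan says: "The investigators are responsible for reporting all adverse events, serious adverse events, and unintended harms within pre-specified times". On how events come to light it says: "Adverse events reported at an assessment visit or informally at any time will be evaluated by the investigators". No closing date for event collection is given.

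The two descriptions of the post-study contact differ. BPA Dose and Duration offers a two-day fresh-food diet or, instead, a "gift card to a natural food market (participant will choose"). Bisphenol A Consumption says that every participant will be given the "diet after they have completed the study (or drop out during the study"). Neither gives a date or mentions a safety question.

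**The concern.** The protocol itself names events that can surface after a participant has gone home. Potential risks to subjects lists nausea, upset stomach and diarrhea from BPA. The section on blood draws and the clamp warns: "There may potentially be a local infection, slight bleeding, or bruising, and fainting in some participants". A catheter-site infection in particular need not be visible when the clamp ends.

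The investigators undertake to report all adverse events, but they can report only what they learn of. During the stay, participants sleep on site with a staff member in the next room, and the clamp is an attended procedure with a physician on call. After the last visit nobody is scheduled to ask. At stake are the care of a healthy volunteer with a late complication and the record of late events in both groups. The insulin-sensitivity comparison is not at stake.

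**Working it through.** The plan gives no figure to reproduce here. The check sets out the schedule and counts what follows the last dose.

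**Dose days.** Two run-in days plus four treatment days, with one dose a day, put the doses on days 3, 4, 5 and 6.

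**Next-morning panels.** A dose on day d has one if a panel falls on day d + 1. Panels fall on days 4 to 6 in one section and on days 3 to 6 in the other. Under both, the doses on days 3, 4 and 5 are covered (by days 4, 5 and 6) and the day-6 dose is not: 3 of 4. The order of the day-6 panel and the day-6 dose is not stated, but no panel falls on a later day.

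**End of the clamp after the last dose.** The inputs are the 1-hour lead (Sequence of Events), and the 90-minute tracer infusion and 120-minute clamp (Muscle Insulin Sensitivity).
- Hour counted to the insulin infusion: 60 + 120 = 180 min = 3 h.
- Hour counted to the tracer infusion: 60 + 90 + 120 = 270 min = 4.5 h.

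**BPA still to be eliminated.** BPA Dose and Duration gives a urinary half-life h of 4 to 5.5 h. Assuming first-order elimination, the fraction left at time t is 0.5^(t/h).

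| t | h = 4 h | h = 5.5 h |
|---|---|---|
| 3 h | 0.595 | 0.685 |
| 4.5 h | 0.459 | 0.567 |
| 24 h | 0.016 | 0.049 |

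Roughly half to two thirds of the last dose is still present when the clamp ends, and 2% to 5% a day after dosing. The protocol's own figure is 92% recovered in urine at 24 hours.

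**Contacts that may follow the clamp.**

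| Contact | What the text settles | Safety question attached |
|---|---|---|
| Night 6 on site | Possible; no discharge time given | No |
| Last urine collection | Days not settled (below) | No |
| Fresh-food diet | Offered with a gift card as alternative, or provided to all; no date | No |
| Physician and staff availability | Depends on the participant getting in touch | No |
| Internal, quarterly and annual safety reviews | Review information already collected | No |

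**Urine.** The outcome section gives 5 collection days and Sequence of Events gives 3 consecutive days for treatment, so I infer 2 at baseline. The treatment collections are then days 3 to 5 or days 4 to 6. If they are days 4 to 6 and the day-6 collection starts with the dose, it ends 24 − 4.5 = 19.5 h to 24 − 3 = 21 h after the clamp. If they are days 3 to 5, it adds 0 h. The text groups these collections with the end-of-treatment assessments, which leans towards days 4 to 6 without deciding it.

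**Count.** Dated adverse-event questions after the clamp in the readable text: 0.

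**The case against.** The strongest reply is that contact probably does not stop at the clamp. The stay is six days with a nightly return, a day-6 urine collection could run most of a day further, and one section gives the diet to all participants. Reports are accepted informally at any time, and staff are available for emergencies. BPA clears quickly, and the preliminary study saw no gastrointestinal distress at this dose. The design figure and consent pages, which might carry a follow-up instruction, cannot be seen.

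Most of this stands, and it makes the gap small. It does not close it, because none of these contacts carries a safety question, the diet has no date, and the informal route depends on the participant. Clearance of BPA also says nothing about a catheter site.

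Three stronger readings are tempting and not supported:
- *That a participant who takes the gift card is never seen again.* One section allows this, but the other provides the diet to everyone, and the two are not reconciled.
- *That participants leave straight after the clamp.* No discharge time is stated.
- *That one later question would make event counts complete.* No dated question is written for the first three doses either, so a question confined to the last dose would not do this. The question needs to look back to the first dose, and even then it rests on recall.

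**Conclusion.** The point holds as a small gap in safety ascertainment. In the readable text, no dated adverse-event question follows the final dose and clamp, and events arising after the participant leaves are captured only if volunteered. The events of most concern are catheter-site infection, bleeding or bruising, and late gastrointestinal symptoms.

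It applies to all 40 randomized participants, or 36 if the expected 10% are lost. The documents give no rate from which to estimate missed events, so I give none. The statistical section plans no between-group comparison of adverse events, so no stated analysis changes.

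A reader might infer that an extra blood panel after the last dose is needed, since the protocol says the effect of repeated dosing on liver and kidney enzymes is unknown. The documents do not carry the point that far: panels already follow one, two and three doses, and the stated elimination is short.

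The conclusion assumes that no follow-up contact appears in the material that is not shown. It is a low-priority improvement.

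**What to change.** Add to Bisphenol A Consumption and to the Data Safety Monitoring Plan wording such as:

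> Between 24 and 48 hours after the last dose taken, including after early withdrawal, blinded staff will ask every participant, by phone or in person and in the same words in both groups, about any adverse event since the first dose. The question will name nausea, upset stomach, diarrhea, fainting, and infection, bleeding or bruising at a catheter site. Informal reports remain open afterwards.

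Attach it to the diet or gift-card contact, or to a final urine return, where that falls in the window; otherwise telephone. It applies whichever post-study option the participant takes. The 24-to-48-hour window is my choice and is not derived from the documents.

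The cost is one short contact each: 40 × 0.9 = 36 up to 40 contacts, at one or two a month on the stated enrollment rate. At an assumed 5 to 10 minutes, that is 36 × 5 / 60 = 3.0 h to 40 × 10 / 60 = 6.7 h of staff time for the whole trial. No extra blood draw is required, and the clamp outcomes are already complete. Naming symptoms may bring in more minor reports, but the same wording in two blinded groups should do so equally.

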3-weeks, a significant treatment x time ($P<0.02$) effect on creatinine-corrected urinary BPS concentrations was observed such that BPS decreased by 1.27 μ g/g creatinine in the intervention group and decreased slightly by 0.09 μ g/g creatinine in the control group. There were no significant changes in BPA concentrations ($P>0.05$).

METHODS

Overview This experimental study is a 2-group randomized, clinical trial comparing a 4-day energy balance diet plus oral BPA consumption at 50 μ g/kg body weight (Diet+BPA) vs. 4-day energy balance diet plus oral placebo consumption (Diet+No BPA). Forty participants will be randomized to Diet+BPA and Diet+No BPA and will reside in a supervised environment at Cal Poly's sleep research facilities in the College of Liberal Arts under the supervision of [name] for 6 days (2-day baseline run-in, followed by 4-day treatment). Main outcome measures (muscle insulin sensitivity and hepatic glucose suppression) will be assessed at baseline and treatment periods.

Experimental Protocol

Participants Forty, 18 to 50 years old, non-dieting, sedentary (≤ 3 hour/week of aerobic exercise), normal-weight (BMI = 18.5 to 24.9 kg/m²) participants will be recruited. All participants will be healthy, weight-stable for the previous 6 months, free of any metabolic or chronic disease, non-smoking, and sedentary, assessed by

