Statistical Analysis The ultimate goal in our analyses will be to compare participants randomized to Diet+BPA vs. Diet+No BPA. We conservatively expect 10% of participants will be lost to follow up. All data will include assessment for model validity (e.g. distribution, homoscedasticity) and will be appropriately transformed to meet model conditions as needed. Outliers will be included in the analysis and, when substantive, their impact on parameter estimates will be noted. Statistical test will be conducted at the P<0.05 level. **Hypothesis 1:** We hypothesize that participants randomized to Diet+BPA will have decreased reduced muscle insulin sensitivity and blunted insulin stimulated hepatic glucose suppression, compared with Diet+No BPA. Under the condition of sphericity, a linear mixed effect model will be used to examine differences in muscle insulin sensitivity and hepatic glucose suppression between groups adjusting for age, sex, education, income, physical activity levels, ethnicity/race, baseline BMI, baseline weight, baseline dietary intake and macronutrient intake. In the event the data do not meet the sphericity condition, multivariate analysis of variance (MANOVA) models with profile analyses will be used with the same covariates. **Hypothesis 2:** Multiple linear regression or repeated measures MANOVA will be used to examine associations between BPA and insulin sensitivity and hepatic glucose suppression adjusting for the same covariates. **Hypotheses 3:** Linear mixed effect model will be used to examine differences in hormones related to the pathogenesis of type 2 diabetes (i.e. C-peptide, Pro-insulin, adiponectin, 17-beta-estradiol). **Exploratory Aim:** Changes in microbiome community structure will be evaluated for each individual by comparing Bray-Curtis similarity measures between samples collected before and after treatment using a linear mixed model.

Timeline The proposed study is currently in review with the American Diabetes Association and National Institutes of Health. We anticipate enrolling 1-2 participants per month with a total of 40 subjects being enrolled through year 3.

PROTECTION OF HUMAN SUBJECTS and DATA SAFETY MONITORING

Proposed level of risk: The risks for physical, psychological, social or legal harm are considered low for all testing procedures and treatment doses. The dose of BPA chosen was based on the US EPA report that that

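### Hypothesis 1 names no treatment contrast and leaves out each outcome's own baseline value; on the likeliest reading the test is valid but gives up some power

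*Combined protocol and SAP*

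**What the plan says.** The Overview under METHODS states: "Main outcome measures (muscle insulin sensitivity and hepatic glucose suppression) will be assessed at baseline and treatment periods". Sequence of Events puts the second assessment of "muscle insulin sensitivity, hepatic glucose suppression, and gut microbiome will occur at the end of the treatment period", and places randomization, blocked by sex and ethnicity, after the baseline assessments. The Outcome Measures section reduces each clamp to one averaged glucose disposal rate (Rd) and one percentage suppression of hepatic glucose production (HGP). Each participant therefore has two values per outcome.

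For Hypothesis 1 the Statistical Analysis section states that "a linear mixed effect model will be used to examine differences in muscle insulin sensitivity and hepatic glucose suppression between groups". The model carries ten covariates, which the plan lists as follows: "adjusting for age, sex, education, income, physical activity levels, ethnicity/race, baseline BMI, baseline weight, baseline dietary intake and macronutrient intake". Baseline BMI, weight and diet are among them; baseline Rd and baseline HGP suppression are not. The text does not say whether the baseline clamp value is a repeated response, part of a change score or unused, and it names no model term as the treatment test. It adds: "In the event the data do not meet the sphericity condition, multivariate analysis of variance (MANOVA) models with profile analyses will be used".

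On numbers, 40 participants are planned, and "We conservatively expect 10% of participants will be lost to follow up". The plan gives no effect size, SD, power or baseline-to-follow-up correlation.

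**The concern.** The main hypothesis of a 40-person trial should say which estimate answers it. Two-visit data allow several: the group-by-time term, the end-of-treatment difference, or that difference adjusted for baseline. They do not have the same power.

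Group-by-time is the likeliest intention. It fits the mixed-model wording and the mention of profile analysis. The team's earlier two-group pre/post trial also reported this term (Preliminary Studies: "a significant treatment x time ($P<0.02$) effect on creatinine-corrected urinary BPS concentrations was observed"). In a randomized comparison it is valid, so what is at stake on that reading is efficiency. With about 36 completers, the baseline clamp value may explain much of the outcome variance. Subtracting it uses that information less well than regressing on it, unless the two values are highly correlated.

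**Working it through.** The plan has no power calculation to reproduce, so this check compares two analyses of the same data.

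**Inputs from the plan.** 40 randomized, 10% lost: 40 × 0.9 = 36 completers. Significance level 0.05.

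**Assumptions.** 1:1 allocation (18 per arm), two-sided testing, equal variance at both visits (set to 1), effect d of 0.5 or 0.8 SD present only at the end of treatment, and r from 0.5 to 0.9. Sex and ethnicity take 1 degree of freedom each and are not prognostic. Ethnicity is counted as 1 because the Participants section sets a Hispanic/non-Hispanic target.

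**Formulas.**
- Group-by-time (change score): variance 2(1 − r), 34 df.
- End-of-treatment value adjusted for baseline, sex and ethnicity (ANCOVA): variance 1 − r², 31 df. Chance imbalance in three covariates inflates the variance by (36 − 3)/(36 − 3 − 3) = 33/30 on average.
- Power from the noncentral t with noncentrality d / √(variance × 2/18).

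**One case in full (d = 0.8, r = 0.5).**
- Group-by-time: variance 1.0, standard error √(2/18) = 0.333, noncentrality 2.40, power 64.5%.
- ANCOVA: 0.75 × 33/30 = 0.825, standard error 0.303, noncentrality 2.64, power 72.6%.

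| d | r | ANCOVA | Group-by-time |
|---|---|---|---|
| 0.8 | 0.5 | 73% | 65% |
| 0.8 | 0.6 | 79% | 74% |
| 0.8 | 0.7 | 87% | 85% |
| 0.8 | 0.8 | 96% | 96% |
| 0.5 | 0.5 | 36% | 31% |
| 0.5 | 0.6 | 41% | 37% |
| 0.5 | 0.7 | 49% | 47% |
| 0.5 | 0.8 | 64% | 64% |

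The gain is 5 to 8 points at r = 0.5, 2 to 3 (before rounding) at r = 0.7, and about 0 at r = 0.8. Simulation at d = 0.8, r = 0.5 (20,000 runs) gave 72.7% and 64.5%.

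**Where the advantage ends.** Setting (1 − r²)(33/30) = 2(1 − r) gives 1 + r = 60/33, so r = 0.818. Allowing for the lower df, the break-even on power is about 0.81 at d = 0.5 and 0.80 at d = 0.8. At d = 0.5 and r = 0.9, ANCOVA has 88.8% and group-by-time 90.3%. Adjusting for baseline alone (inflation 33/32) moves the variance break-even to 64/33 − 1 = 0.94 and gives 90.8% in that same case.

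**Sphericity.** Two visits give one within-person difference, so there is only one variance and nothing it could be unequal to. The df of Mauchly's test is k(k − 1)/2 − 1 = 0 at k = 2. The condition cannot fail, and the MANOVA branch is never reached.

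**The case against.** The strongest reply is that group-by-time is valid and that preferring ANCOVA is a choice about efficiency, resting on values of r and d that the documents do not give. That is right, and the point is put no higher than that. The documents also hint that r could be high for Rd. Rd is expressed in mg/min, not per kg, and the same person is measured twice within a controlled six-day stay, so body size would enter both values. This is an inference, and it does not carry over to HGP suppression, which is a ratio. It does mean that the gain for Rd may be small or nil.

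A reader might infer something worse: a group main effect over both visits, which averages in a pre-treatment difference expected to be zero. It would halve the effect, with variance (1 + r)/2, and give only 23–27% power at 0.8 SD and 12–13% at 0.5 SD for r from 0.5 to 0.8. The words do not exclude this, but the documents do not support it as the intention. The baseline clamp precedes randomization, and the comparable parallel-group trial reported treatment by time. The pilot's main effects of condition came from a cross-over, where they are appropriate.

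A reader might also infer an inflated false-positive rate, 1 − 0.95² = 9.75% per outcome if either term could be claimed. That needs the term to be chosen after seeing the data, and equal variances at the two visits. Nothing in the plan proposes such a choice.

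The ten listed covariates are not shown to do harm either. On the group-by-time reading, with complete data, those that are constant over time and entered as main effects cancel from the contrast.

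**Conclusion.** The point holds as a matter of specification and efficiency. The contrast and the role of the baseline clamp value are not stated. Against the likeliest reading, baseline adjustment is worth about 5 to 8 points of power at r = 0.5, 2 to 3 at r = 0.7 and about 0 at r = 0.8. Above r of about 0.80 to 0.82 it costs about 1 to 2 points at 0.5 SD if sex and ethnicity are not prognostic. These figures rest on 18 per arm, two-sided 0.05, equal visit variances and effects of 0.5 to 0.8 SD, none of which except the completer count comes from the plan.

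The documents do not support saying that the planned test is invalid or that its error rate is inflated. The inoperative sphericity clause changes no result.

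**What to change.** For Rd and for HGP suppression separately, name one primary test: the arm difference in the end-of-treatment value, adjusted for that outcome's own baseline value and for the blocking factors sex and ethnicity.

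State one fitting method. Either use ANCOVA in completers, or use a mixed model with a common baseline mean, which keeps participants who have only a baseline clamp. With the expected 10% loss the two can differ, so they should not be offered as interchangeable.

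The cost is wording in the Statistical Analysis section. Both clamps, sex and ethnicity are already planned, so no visit or assay is added. The downside is the small loss at high r given above; adjusting for baseline alone removes nearly all of it, at the price of leaving out the blocking factors.

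The sphericity/MANOVA sentence may be deleted as a tidy-up. Moving the remaining covariates to a sensitivity analysis is optional and not needed for this fix. The power figures here are for the model without them and would need recomputing if they stay in it.
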